PROTOCOL TITLE: Measuring Dysphagia after ACS Surgery

PROTOCOL TITLE:

Feasibility Assessment of A Novel Wearable Skin Sensor for Post-Operative Monitoring Following Anterior Cervical Discectomy and Fusion (ACDF)

PRINCIPAL INVESTIGATOR:

[name]
Northwestern University
Department: Department of Orthopaedic Surgery
[contact]
[contact]

VERSION DATE: 02/01/2021

1.0 Purpose of the Study:

The purpose of this study is to assess the function and reliability of a non-invasive, skin-like electronic sensor. We hypothesize that this skin sensor will address an unmet need to wirelessly and noninvasively monitor and characterize the recovery process in post-operative patients who have undergone anterior cervical discectomy and fusion (ACDF). Specifically, we will validate the use of the sensor in this patient population through monitoring of key physiological signals in the recovery process, including heart rate, respiratory rate, swallow count, talking time, energy expenditure, neck specific motion, and body orientation.

2.0 Background / Literature Review / Rationale for the study:

Dysphagia, dysphonia, and loss of cervical range of motion (ROM) are common complications after anterior cervical spine surgery, specifically anterior cervical discectomy and fusion (ACDF). Despite their clinical importance, studies on the treatment and/or prevention of these complications are limited due to the lack of valid and reliable outcome measures. The majority of research is found in the otolaryngology literature and has focused on disease pathophysiology, diagnosis, and therapy.

Dysphagia and dysphonia are widely measured by patient self-reported questionnaires, including the MD Anderson Dysphasia Inventory and SWAL-QOL. However, these validated outcome tools are cumbersome to complete and, therefore, have not been widely accepted into clinical practice, including in post-operative ACDF patients. The Bazaz score, a subjective questionnaire that has not been validated in the literature, has also been used to evaluate dysphagia after ACDF. Assessment using the Bazaz score is based on clinical examination, with the surgeon listening to the patient's voice and documenting hoarseness in

PROTOCOL TITLE: Measuring Dysphagia after ACS Surgery

the post-operative period. Recently, new patient-centered outcomes, the Eating Assessment Tool (EAT-10) and Voice Handicap Index (VHI-10) have been developed. Both EAT-10 and VHI-10 have excellent validity and reliability in evaluating dysphagia and dysphonia, respectively, in post-operative ACDF patients and can be used to document the initial dysphagia or dysphonia severity and monitor the treatment response in people with a wide array of swallowing and voice disorders. However, these methods of evaluating dysphagia and dysphonia alone offer limited information about the severity and characteristic of dysphagia or dysphonia and do not provide continuous monitoring of swallowing or speaking function throughout the post-operative period.

The wearable sensors under investigation in this study offer a novel, non-invasive, and easy-to-use way to monitor dysphagia, dysphonia, cervical ROM, and overall recovery progress in post-operative ACDF patients. Previous testing has demonstrated the ability of our sensors to monitor vital signs (including heart rate and respiratory rate), swallow count, talking time, energy expenditure, cervical neck movement, and body orientation. Sensor-measured swallow count and talking time, in conjunction with EAT-10 and VHI-10 scores, can provide a comprehensive view of the progression of dysphagia and dysphonia. Cervical neck movements measured by the sensor can enable continuous assessment of cervical ROM. Other general metrics captured by the sensors, including heart rate, respiratory rate, energy expenditure, and body orientation can provide other meaningful measures of recovery in post-operative ACDF patients. Our sensors have also received positive feedback from patients and physicians on their comfort, ease of use, and application, further demonstrating the potential value of these sensors in improving the quality of post-operative care for ACDF patients.

3.0 Inclusion and Exclusion Criteria:

Inclusion criteria:

- Patients who have undergone anterior cervical discectomy and fusion (ACDF) for one or more levels for a diagnosis of cervical radiculopathy or myelopathy
- Scheduled to return to the MSK orthopaedic clinic for a post-operative appointment
- Over 18 years of age at the time of consent

Exclusion criteria:

- Patients that underwent a revision of previous ACDF surgery at one or more operative levels
- Surgeries performed for a traumatic or oncologic etiology
- Members of vulnerable populations (i.e. prisoners, pregnant women)
- Patients unable or unwilling to consent to participate in the study

PROTOCOL TITLE: Measuring Dysphagia after ACS Surgery

4.0 Sample Size:

We anticipate 30 individuals will participate at Northwestern Memorial Hospital in this study and will take approximately 6 months to recruit.

5.0 Research Locations:

The enrollment and data collection for this study will take place in the MSK orthopaedic clinic at [name] and participants will wear the skin sensor during the intervening week between discharge and post-operative follow up visit with their surgeon.

6.0 Multiple sites:

N/A

7.0 Reliance Agreements/Single IRB:

N/A

8.0 Procedures Involved:

Once eligible participants have endorsed the informed consent and HIPAA authorization, they will undergo their planned ACDF procedure at NMH. During closeout of the procedure the attending surgeon will then place the skin sensor into position on the suprasternal notch. Collection of the physiological data elements expanded below will begin as the participant is transferred to the post-anesthesia care unit:

- Heart rate
- Respiratory rate
- Cervical axis range of motion
- Talking time
- Swallowing frequency
- Caloric consumption
- Body positioning

The participant will continue to wear the skin sensor during the intervening 2 weeks until they return to clinic for their standard-of-care visit with the attending surgeon. Upon returning to clinic the surgeon will perform their assessment of the participant's progress in recovery and the skin sensor will be removed for download of the data elements collected between discharge and the participant's return to clinic.

An optional component for video recording of the sensor device functioning once applied will be offered to participants in order to assist with data analysis and development of figures and/or diagrams mapping the data obtained by the sensor to physiological behavior recorded in real time. This component will not

PROTOCOL TITLE: Measuring Dysphagia after ACS Surgery

be obligatory for participation and individuals wishing to enroll in the study without consenting to video recording will be instructed to indicate their refusal on the relevant section of the consent form.

The participant will then be asked to complete a brief questionnaire within the study associated REDCap project regarding their experience/satisfaction wearing the sensor following their surgery. The sensor data and qualitative surveys will be compared to the clinical report provided by the attending surgeon as part of the terminal analysis.

9.0 Incomplete Disclosure or Deception:

N/A

10.0 Recruitment Methods:

Potential participants for this study will be identified by [name] and [name] using the surgical schedule to monitor for upcoming candidates for ACDF surgery. Once the surgery has been confirmed for the schedule, eligible participants will be approached prior to surgery to introduce the study and gauge interest to participate, where after those patients who agree to participate will be asked to sign a copy of the informed consent and HIPAA authorization form.

11.0 Consent Process:

Eligible participants identified by the study team and attending surgeon will be approached in the pre-operative holding area on the day of surgery to be introduced to the study and have any questions regarding participation answered. Risks, benefits, and alternatives of participation in the study as well as the ability to withdraw participation at any time will be discussed with the participant. Once they have agreed to participate in the study, they will be provided with an electronic copy of the informed consent and HIPAA authorization form via the REDCap application to review and endorse. All participants will be offered the opportunity to have a PDF copy of the endorsed consent emailed to the address on file at any time.

12.0 Financial Compensation:

There is no payment for participating in this study and the risks of the study are minimal.

13.0 Audio/Video Recording:

N/A

14.0 Potential Benefits to Participants:

PROTOCOL TITLE: Measuring Dysphagia after ACS Surgery

There may be no benefit from being in this research, but there is hope that what we learn may be helpful to future patients or society in general.

15.0 Risks to Participants:

The risks of the study are minimal. The primary risk associated with participation is discomfort from the skin sensor placed on the suprasternal notch following surgery. Any discomfort or irritation caused by the sensor that the participant deems excessive may lead the study team to remove the sensor prior to discharge or prior to the 2-week post-operative visit at the participant's discretion.

An additional risk is a potential loss of participant privacy from the data collected during the conduct of the study. The study team has taken measures described below to minimize this risk and all study data will be de-identified at the earliest possible opportunity to further protect the participants.

16.0 Provisions to Protect the Privacy and Confidentiality of Participants and the Research Data:

All data elements that are PHI identifiers will be stored separately from randomly generated participant ID numbers on a secure, encrypted NU SharePoint site and/or a REDCap project. Access to participant information will be restricted only to the PI, co-I, and members of the IRB approved authorized personnel list for the study. Participants will be able to ask any questions regarding the research before consent & the research staff will be transparent with explaining the study and explaining the timeline for participants.

The importance for confidentiality of the participant's protected health information (PHI) is recognized. PHI will be collected and transferred only where necessary. Where possible, participants will be identified only by generic ID's. SSL encryption will be used with all internet web pages to ensure confidential form submission. For data files that need to be transferred electronically, the information will be encrypted prior to transport. The web servers and associated database servers will be housed on dedicated housed with NU SharePoint. These will be physically protected from intrusion as well as natural disasters. The secure facilities are protected electronically by hardware and software firewalls, intrusion detection software, anti-virus scans, and 24x7 monitoring by onsite professionals.

17.0 Data Monitoring Plan to Ensure the Safety of Participants:

N/A

18.0 Data, and if applicable, Specimen Banking:

PROTOCOL TITLE: Measuring Dysphagia after ACS Surgery

Confidentiality of patient information will be maintained using the REDCap database and NU SharePoint site associated with this study. Access to this database will only be available to the PI, co-I, and members of the IRB approved authorized personnel list. All study data will be maintained in a de-identified manner for a period of no less than 3 years following completion of data collection per NU policy. The data will thereafter be destroyed in its entirety via electronic deletion.

19.0 Data Sharing:

N/A

20.0 Qualifications to Conduct Research and Resources Available:

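### Section 1 promises reliability and validation of the sensor on seven signals, but Section 8 requires no time-matched reference for any of them, so only feasibility can be concluded

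*Protocol*

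**What the plan says.** The protocol title calls the study a "Feasibility Assessment of A Novel Wearable Skin Sensor for Post-Operative Monitoring". Section 1 sets the purpose: "The purpose of this study is to assess the function and reliability of a non-invasive, skin-like electronic sensor". It then becomes more specific: "we will validate the use of the sensor in this patient population through monitoring of key physiological signals in the recovery process". Seven signals follow: heart rate, respiratory rate, swallow count, talking time, energy expenditure, neck motion and body orientation. Section 2 adds that earlier testing showed the sensors able to monitor these signals.

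Section 8 gives the procedures. The surgeon places one sensor at the end of the operation. "Collection of the physiological data elements expanded below will begin as the participant is transferred to the post-anesthesia care unit". At the return visit "the surgeon will perform their assessment of the participant's progress in recovery". For the recorded data, the same section says that "the skin sensor will be removed for download of the data elements collected between discharge", with the clinic visit as the end of that period. The participant completes a questionnaire on the experience of wearing the device. Sensor data and survey answers are then compared with the surgeon's clinical report.

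Section 8 also offers an optional video, meant to help map sensor output to behaviour seen in real time. Section 13, on audio and video recording, reads N/A. On sample size, Section 4 says only: "We anticipate 30 individuals will participate at Northwestern Memorial Hospital in this study".

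**The concern.** In measurement work, *validate* normally means agreement with a reference, and *reliability* normally means repeatability. The protocol uses the words in that sense elsewhere: Section 1.0's companion background in Section 2.0 complains that the field lacks valid and reliable outcome measures, and credits two questionnaires with both properties. A reader may take the purpose statement the same way.

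The required procedures do not produce the data for that reading. If the study runs as written and reports that the sensor was validated, or proved reliable, in ACDF patients in the measurement sense, nothing collected under Section 8 as a requirement would support the statement. An analysis plan decides how collected data are analysed. It cannot recover a video that was not taken or in-hospital sensor data that were not kept.

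**Working it through.** The protocol gives no statistical figure to reproduce, because the 30 participants are an anticipated enrolment without a precision or power target. The check sets the aim against the procedures.

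**Step 1. Signals and references.** Section 1 names seven signals and Section 8 lists seven matching data elements.

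| Signal in Section 1 | Data element in Section 8 | Required time-matched reference | Possible source under the fix |
|---|---|---|---|
| Heart rate | Heart rate | None | Charted value, if charted |
| Respiratory rate | Respiratory rate | None | Charted value, if charted |
| Swallow count | Swallowing frequency | None | Consented video, where swallows can be seen |
| Talking time | Talking time | None | Consented video |
| Energy expenditure | Caloric consumption | None | None identified |
| Neck motion | Cervical range of motion | None | None identified for the range itself |
| Body orientation | Body positioning | None | Consented video |

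Required references: 0 of 7. How many signals gain one under the fix depends on charting and video uptake, which the protocol does not give.

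**Step 2. The one required comparison.** The surgeon's report follows a visit described as an assessment of recovery progress. Nothing says that it measures any of the seven signals. It belongs to a single visit at the end of wear, whereas the sensor records throughout. The questionnaire concerns the experience of wearing the device and is no reference either.

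**Step 3. What sensor data alone can identify.** Write a reading as Y = T + b + e, where T is the true value, b the sensor's systematic error and e its random error, taken as independent of T.

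- The mean of Y gives E(T) + b. Without a reference for T, b cannot be separated out, whether 30 or 3,000 people are enrolled.
- The variance of Y gives Var(T) + Var(e). Comparable periods within one person's wear could help to describe short-term consistency, but they say nothing about b.
- With no second sensor and no re-placement, variation due to device or placement cannot be told apart from differences between participants.

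**Step 4. The optional comparator.** Section 8 offers video and Section 13 says N/A. Both cannot describe the same study. Even if video is taken, it is voluntary, and its timing and amount are not stated.

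**Step 5. The download window.** Section 8 starts collection at PACU transfer but describes the downloaded data as running from discharge to clinic. Section 5 also describes wear from discharge. Read literally, this leaves out the hospital stay, the period in which charted vital signs could serve as a reference.

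**The case against.** The strongest reply is that this is a feasibility study and says so in its title. Section 1 speaks of validating *use*, through monitoring, and states no accuracy or agreement endpoint. Section 2 presents the ability to measure as already shown by previous testing. On that reading, aim and procedures agree and only the wording needs attention. Much of this stands: the feasibility reading is open, and it is the one the data support. But Section 1 does not confine itself to it, and earlier evidence of ability is not validation in this patient population, which is what Section 1 promises.

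Four stronger readings are tempting and are not supported:

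- A reader might infer that EAT-10 and VHI-10 were promised and then left out. Section 2 mentions "Sensor-measured swallow count and talking time, in conjunction with EAT-10 and VHI-10 scores" only as rationale for what the sensor could offer. Their absence from Section 8 is not a contradiction, and such scores would not be a time-matched reference for swallow counts.
- A reader might infer that no repeat measurement could ever be derived. Continuous wear may allow similar periods within a person to be compared. What is missing is a second sensor or a re-placement.
- A reader might infer that in-hospital data will be discarded or that no video will be taken. The text is unclear on the first and contradictory on the second. It establishes neither.
- A reader might size the defect by the precision of limits of agreement at some number of participants. The protocol plans no such analysis, so those figures would describe a proposed analysis and not the gap.

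**Conclusion.** The point holds in a limited form and should be fixed. As written, the study can show that the sensor can be worn, operates and captures data in ACDF patients after surgery. It cannot show that any of the seven signals is accurate in them. The size is a count, 0 of 7 signals with a required time-matched reference, and a larger sample would not change it.

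This rests on Section 8 being the full list of required procedures and on the surgeon's report, whose content is not stated, not holding time-matched values of the signals. The Section 8 and Section 13 conflict over video, and the unclear download window, are visible on the page and need no assumption. The study can still run; what is at risk is the conclusion drawn from it.

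**What to change.** 1. In Section 1, state the purpose as feasibility, dependable operation and data completeness, and limit *validate* to signals that will have a reference.
2. Reconcile Section 13 with the optional video in Section 8.
3. State that the download covers data from PACU transfer onward.
4. Where heart rate and respiratory rate are charted in hospital (an assumption; the protocol does not say), compare them with time-matched sensor values by bias and limits of agreement, allowing for repeated readings per participant.
5. For participants who consent to video, have the existing team score visible behaviours without sight of the sensor output. Report the result as descriptive, with the number contributing.

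Items 1 to 3 are text changes that rest on the protocol alone; items 4 and 5 depend on charting and on video uptake. The cost is one amendment, some chart extraction and clip review, and a narrower stated claim. No patient procedure is added. It should be checked that the consent and HIPAA authorization cover chart extraction, since those forms are not at hand.

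Limits remain. Agreement would be tested only in hospital, at the charted times, and in video consenters, who may differ from those who decline. Swallows may not be visible on unstructured video. For signals left without a reference, the claim stays at feasibility.

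### Does the past-tense wording of the eligibility criteria conflict with consent before surgery in a way that needs a change?

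*Protocol*

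**What the plan says.** Section 3.0 lists three inclusion and four exclusion criteria. The first inclusion criterion is "Patients who have undergone anterior cervical discectomy and fusion (ACDF) for one or more levels for a diagnosis of cervical radiculopathy or myelopathy". The first exclusion is "Patients that underwent a revision of previous ACDF surgery at one or more operative levels" and the second is "Surgeries performed for a traumatic or oncologic etiology". Only the age criterion carries a time of assessment: "Over 18 years of age at the time of consent".

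Section 5.0 states: "The enrollment and data collection for this study will take place in the MSK orthopaedic clinic". The same sentence goes on to say that the sensor is worn between discharge and the follow-up visit.

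Section 8.0 gives the order of events: "Once eligible participants have endorsed the informed consent and HIPAA authorization, they will undergo their planned ACDF procedure at NMH". The surgeon places the sensor at closeout, and "Collection of the physiological data elements expanded below will begin as the participant is transferred to the post-anesthesia care unit". The sensor is taken off and its data downloaded at the clinic visit.

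Section 10.0 has candidates identified "using the surgical schedule to monitor for upcoming candidates for ACDF surgery" and approached before the operation. Section 11.0 places the approach and consent in the pre-operative holding area on the day of surgery.

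**The concern.** Sections 8.0, 10.0 and 11.0 all call patients eligible before they have been operated on, yet the first criterion in Section 3.0 is worded so that only a completed operation satisfies it. If that criterion is applied at consent, a patient awaiting a first ACDF fails it, and following the recruitment procedure breaches the eligibility rule. With 30 participants anticipated, a strict auditor could in principle log a technical deviation for every one of them.

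Section 5.0 seems to add a second conflict. It names the clinic for enrollment and data collection, while consent is taken in the holding area and recording starts in hospital.

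The matter would be serious if the conflict left it unclear who belongs in the study population, or if two staff members following different sections would enroll different patients.

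**Working it through.** No arithmetic beyond a count applies, so the check compares the sections.

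**Count of criteria (Section 3.0).** 3 inclusion + 4 exclusion = 7.
- Plainly worded for a completed operation: the ACDF inclusion and the revision exclusion, so 2 of 7.
- The trauma and cancer exclusion names a type of surgery by its reason. It reads equally well for an operation that is planned. Counting it gives at most 3 of 7.
- With a stated time of assessment: age only, 1 of 7.

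**When the ACDF criterion is tested.** No section ties it to consent. Two readings are possible.

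| Step | Criterion describes the monitored patient | Criterion tested literally at consent |
|---|---|---|
| Identified from the surgical schedule (10.0) | Candidate for ACDF | Not yet qualified |
| Consent in the holding area (11.0) | Consents to a study of recovery after ACDF | Not yet qualified |
| Sensor placed at closeout (8.0) | ACDF being completed | Never reached for a first ACDF |
| Recording from transfer to post-anesthesia care (8.0) | ACDF done, criterion met | Never reached for a first ACDF |

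The literal reading leaves no patient with a first ACDF to study and cannot be combined with sensor placement in the operating room. The other reading fits every procedural section. It also fits Section 1.0, which describes the target population as post-operative patients. Staff therefore have only one workable interpretation.

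**Does the wording change who is monitored?**
- Planned first ACDF carried out for radiculopathy or myelopathy: monitored under past-tense or future-tense wording.
- Planned revision, or surgery for trauma or cancer: excluded under either wording.
- Operation cancelled after consent: no closeout, so no sensor is placed and no sensor data arise, under either wording.
- Operation turns out to be a revision or to have an excluded cause: the past-tense criteria apply to the operation actually done, so they already exclude this patient from the population of interest.

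None of the four cases ends differently because of the tense.

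**Location (Section 5.0).** Data collection in the clinic is compatible with Section 8.0, which puts the surgeon's assessment, sensor removal and download there. Section 5.0 itself has the sensor worn outside the clinic, so it does not confine recording to the clinic. What remains is the place of enrollment: clinic in Section 5.0, holding area in Section 11.0. Section 10.0 says only that the approach comes before surgery and names no place. Nothing the protocol measures or compares depends on the room in which consent was signed.

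The different lengths of sensor wear given in Sections 5.0 and 8.0 are a separate matter and play no part here.

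**The case for a change.** The strongest case for acting is that Section 3.0 is the eligibility rule and should be correct as written. Sections 8.0, 10.0 and 11.0 use the word eligible before surgery, which weakens the reading that the criterion only describes patients once monitored. No sentence says that the criterion is confirmed afterwards. Compliance is judged on the written criterion, and rewording would cost little.

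Part of this stands. The tense of two criteria does not match the order of events, and the place of enrollment in Section 5.0 does not match Section 11.0.

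The claimed consequence does not stand. A deviation for every participant requires the ACDF criterion to be assessed at consent, and the protocol says that of age alone. The contrast between the age criterion and the others supports the descriptive reading at least as well. Re-confirming eligibility at sensor placement would go beyond rewording: it would add an intraoperative check that the protocol does not contain and that the mismatch does not require.

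**Conclusion.** This is a clerical slip with no gain from correcting it. Two of seven criteria (three on the widest count) are worded for surgery already done, and one location is misstated. Three sections agree on consent before the operation, so the intended design is plain. Patients enrolled and monitored are the same under either wording, and there is no bias or loss of precision to remove.

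The conclusion assumes that staff follow Sections 8.0, 10.0 and 11.0, the only sections that set out how recruitment and sensor placement are carried out. It also assumes that the ACDF criterion describes the operation after which the patient is monitored. On those assumptions, nothing the study does or can conclude depends on the wording.
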